13.2 Data Management Responsibilities

Any source documents and laboratory reports must be reviewed by the clinical team and data entry staff, who will ensure their accuracy and completeness. AEs must be recorded on the appropriate data collection form, assessed for severity and relationship, and reviewed by the site principal investigator or appropriate sub-investigator. AEs must be graded based on the FDA Guidance for Industry: *Toxicity Grading Scale for Healthy Adult and Adolescent Volunteers Enrolled in Preventive Vaccine Clinical Trials* September 2007, as modified for this study and as appropriate for the administration of rezafungin; see [Appendix B](#).

Electronic data capture is the responsibility of the clinical trial staff at the site under the supervision of the site PI. During the study, the PI must maintain complete and accurate documentation for the study.

Data collection is the responsibility of the study personnel at the participating clinical study site under the supervision of the site principal investigator. During the study, the site principal investigator must maintain complete and accurate documentation for the study.

The data coordinating center for this study, Emmes, will be responsible for data management, quality review, analysis, and reporting of the study data.

13.3 Data Capture Methods

Clinical data (including, but not limited to, AEs, physical assessments, clinical laboratory values, and concomitant medications) will be entered into AdvantageEDCSM, a 21 CFR Part 11-compliant EDC system managed by Emmes. AdvantageEDCSM access is password protected. Access is granted to specific individuals based on the roles identified for this trial. The site enters the data into AdvantageEDCSM from the DCFs completed by the study personnel. Data are validated through a query resolution process, comprising both automated and manual queries.

13.4 Types of Data

Data for this trial will include but are not limited to all data for safety and PK deemed necessary for the analysis per protocol, demographic data, ECG data, clinical laboratory values, concomitant medications, AEs, photographs, and medical history.

13.5 Study Records Retention

Trial documents will be retained for at least 2 years after the last approval of a marketing application in an ICH region and until there are no pending or contemplated marketing applications in an ICH region or at least 2 years have elapsed since the formal discontinuation of clinical development of the study drug. These documents will be retained for a longer period, however, if required by local regulations. No records will be destroyed without the written consent of the Sponsor. It is the responsibility of the Sponsor to inform the Site PI when these documents no longer need to be retained.

14 CLINICAL MONITORING

14.1 Site Monitoring Plan

Site monitoring is conducted to ensure that the human subject protections, trial and laboratory procedures, trial intervention administration, and data collection processes are of high quality and meet Sponsor, ICH/GCP guidelines, and applicable regulations, and that this trial is conducted in accordance with the protocol, protocol-specific MOP, and applicable Sponsor SOPs. DMID, the Sponsor, or its designee will conduct site-monitoring visits as detailed in the clinical monitoring plan.

Site visits will be made at standard intervals as defined by DMID and may be made more frequently as directed by DMID. Monitoring visits will include, but are not limited to, review of regulatory files, accountability records, eCRFs, ICFs, medical and laboratory reports, and protocol and GCP compliance. Site monitors will have access to each site, trial personnel, and all trial documentation according to the DMID-approved site monitoring plan. Trial monitors will meet with Site PI to discuss any problems and actions to be taken and will document site visit findings and discussions.

15 PUBLICATION POLICY

All investigators funded by the NIH must submit or have submitted for them to the National Library of Medicine's PubMed Central (<http://www.ncbi.nlm.nih.gov/pmc/>) an electronic version of their final, peer-reviewed manuscripts upon acceptance for publication, to be made publicly available no later than 12 months after the official date of publication. The NIH Public Access Policy ensures the public has access to the published results of NIH funded research. It requires investigators to submit final peer-reviewed journal manuscripts that arise from NIH funds to the digital archive PubMed Central upon acceptance for publication. Further, the policy stipulates that these papers must be accessible to the public on PubMed Central no later than 12 months after publication.

Refer to:

- NIH Public Access Policy, <http://publicaccess.nih.gov/>
- NIH Office of Extramural Research (OER) Grants and Funding, <http://grants.nih.gov/grants/oer.htm>

As of January 2018, all clinical trials supported by the NIH must be registered on ClinicalTrials.gov, no later than 21 days after the enrollment of the first subject. Results of all clinical trials supported by the NIH, generally, need to be submitted no later than 12 months following the primary completion date. A delay of up to 2 years is available for trials that meet certain criteria and have applied for certification of delayed posting.

As part of the result posting a copy of this protocol (and its amendments) and a copy of the Statistical Analysis Plan will be posted on ClinicalTrials.gov.

For this trial the responsible party is DMID, which will register the trial and post results.

The responsible party does not plan to request certification of delayed posting.

Refer to:

- Public Law 110-85, Section 801, Clinical Trial Databases
- 42CFR11
- NIH NOT-OD-16-149

17 APPENDICES

Appendix A. Schedules of Events

Table 11: Schedule of Study Procedures and Evaluations for Cohorts 1-6 in SAD (Part 1)

Procedures/Day	Screening	Baseline Check-in	Inpatient – Confined to CRU							FU	Phone FU	FU/ET	Unscheduled
	-28 to -2	-1	1	2	3	4	5	6	7	14 (±1)	21 (±1)	30 (±1)	
Informed Consent Form ^a	X												
Assessment of Eligibility Criteria	X	X											
Demographics	X												
Height ^b , Weight, BMI	X	X										X	
Review of Medical History	X	X											
Hepatitis and HIV tests ^c	X												
Follicle-stimulating hormone(FSH) test ^d	X												
Pregnancy test ^e	X	X										X	
Review of Concomitant Medications	X	X	X		X		X		X	X			X X
Study drug randomization just prior to dosing ^f			X										
Administration of study drug ^g			X										
Vital signs ^h	X	X	X X		X		X		X	X		X X	
Physical examination ⁱ	X	X	X X		X		X		X			X X	
12-lead ECGs ^j	X		X						X			X X	
Blood for hematology & coagulation ^k	X	X		X				X				X X	
Blood for chemistry panel ^k	X	X		X				X				X X	
Urine for urinalysis, drug screen, alcohol ^l	X	X		X				X				X X	
Urine cotinine	X	X											

Procedures/Day	Screening	Baseline Check-in	Inpatient – Confined to CRU							FU	Phone FU	FU/ET	Unscheduled
	-28 to -2	-1	1	2	3	4	5	6	7	14 (±1)	21 (±1)	30 (±1)	
Blood for PK analysis ^m			X	X	X		X		X	X		X	
Reactogenicity evaluation ⁿ			X	X	X	X	X	X	X	X	X	X	X
Assessment for AEs ^o			X	X	X	X	X	X	X	X	X	X	X
Counsel/reminders ^p	X									X	X	X	
Memory Aid ^q			X							X	X	X	X

Abbreviations: AE: adverse event; BMI: body mass index; CRU: clinical research unit; ECG: electrocardiogram; FU: follow-up; HIV: human immunodeficiency virus; PK: pharmacokinetic.

- a. Informed consent will be obtained before initiating any trial-related assessments and procedures,
- b. Height at Screening only,
- c. Screen (serum) for hepatitis B surface antigen, hepatitis C virus antibody, and HIV antibody,
- d. Perform FSH (serum) test in postmenopausal females only,
- e. Perform serum pregnancy tests at Screening, Day -1, and Day 30 females only,
- f. Randomize subjects on Day 1 just before dosing,
- g. A single dose of study drug will be administered via SC injection on Day 1,
- h. Vital signs will be obtained at Screening; on Day -1, on Day 1 prior to study drug administration (within 60 minutes prior to study drug) and at 15 minutes (±5 min), 1 hour (±10 min) and 2 hours(±10 min) post-dose; at 24, 72, 144 hours (±30 min), post-dose(Days 2, 4, and 7), and Days 14 (±1 day), and 30 (±1 day),
- i. A complete PE will be performed at Screening and targeted PEs will be performed on Days -1, 1, 2, 4, 7, and 30 (±1 day),
- j. ECGs will be obtained at Screening and on Day 1 within 60 minutes prior to study drug administration, and 4 hours (± 10 minutes) post-dose, Day 7, Day 30, and Uncheduled visits
- k. Fasting (at least 8 hours) blood samples will be collected for hematology, coagulation and chemistries at Screening and on Days -1, 2, 7, and 30 (±1 day), Hematology tests consist of CBC with differential; coagulation tests consist of PT/PTT/INR; Chemistries panel includes albumin, glucose, blood urea nitrogen or urea, potassium, calcium, sodium, chloride, total protein, creatinine, CO2, CK, phosphorus, alkaline phosphatase, AST, ALT, total bilirubin, direct bilirubin,
- l. Urine will be collected for urinalysis, urine drug screen and urine alcohol at Screening and on Day -1. Urine will be collected for urinalysis on Days 2, 7, and 30 (±1 day),
- m. Collect PK blood samples within 60 minutes before study drug dosing and at 0.5 (±5 min), 1, 2, 4, 6, 8, and 12 hours (±10 min),on (Day 1; 24 hours (±30 min) on Day 2; 48 hours (±30 min) on Day 3; 96 hours (±30 min) onDay 5; and 144 hours (±30 min) onDay 7 after dosing; and on Days 14 (±1 day) and 30 (±1 day), (No PK blood sample collection for Cohort 1)

- n. Injection site assessment pre-dose and at 1 and 4 (\pm 10 min), 24, 48, 72, 96, 120, and 144 h (\pm 30 min) post dose, Day 14 (\pm 1 day), Day 21 (\pm 1 day), and Day 30 (\pm 1 day). Unscheduled visits are not timed.
- o. Subjects are to be assessed for AEs occurring from the time of the first dose of study drug through Day 30 (\pm 1 day),
- p. Counsel/reminder on contraceptive use and post-discharge instructions (dietary and medication/nonmedication vaccine and blood/blood product/sperm donation restrictions); as described in [Section 5.1](#).
- q. Memory Aid issued on Day 1, training on Day 7, and review on Days 14, 21, and 30 and at Unscheduled visits.

Table 12: Schedule of Study Procedures and Evaluations for Cohorts 7-10 in MAD (Part 2)

Procedures/Day	Screening	Baseline Check-in	Inpatient – Confined to CRU							FU	FU/ET	Unscheduled	
			1	2	3	4	5	6	7				
	-28 to -2	-1	8	9	10	11	12	13	14	30 (\pm 1)	45 (\pm 1)		
			15	16	17	18	19	20	21				
Informed Consent Form ^a	X												
Assessment of Eligibility Criteria	X	X	X										
Demographics	X												
Height ^b , Weight, BMI	X	X									X	X	
Review of Medical History	X	X											
Hepatitis and HIV tests ^c	X												
Follicle-stimulating hormone (FSH) test ^d	X												
Pregnancy test ^e	X	X									X		
Review of Concomitant Medications	X	X	X	X	X	X	X	X	X	X	X	X	
Study drug randomization just prior to dosing ^f			X										
Administration of study drug ^g			X										
Vital signs ^h	X	X	X	X	X	X	X	X	X	X	X	X	
Physical examination ⁱ	X	X	X	X	X	X	X	X	X	X	X	X	

Procedures/Day	Screening	Baseline Check-in	Inpatient – Confined to CRU							FU	FU/ET	Unscheduled	
			1	2	3	4	5	6	7				
	-28 to -2	-1	8	9	10	11	12	13	14	30 (±1)	45 (±1)		
			15	16	17	18	19	20	21				
12-lead ECGs ^j	X		X							X	X	X	
Blood for hematology & coagulation ^k	X	X		X						X		X	
Blood for chemistry panel ^k	X	X		X						X		X	
Urine for urinalysis, drug screen, alcohol ^l	X	X		X						X		X	
Urine cotinine	X	X											
Blood for PK analysis ^m			X	X	X		X			X	X		
Reactogenicity evaluation ⁿ			X	X	X	X	X	X	X	X	X	X	
Assess for AEs ^o			X	X	X	X	X	X	X	X	X	X	
Counsel/reminders ^p	X									X	X		
Memory Aid ^q			X							X	X	X	

Abbreviations: AE: adverse event; BMI: body mass index; CRU: clinical research unit; ECG: electrocardiogram;

FU: follow-up; HIV: human immunodeficiency virus; PK: pharmacokinetic.

- a. Informed consent will be obtained before initiating any trial-related assessments and procedures,
- b. Height at Screening only,
- c. Screen (serum) for hepatitis B surface antigen, hepatitis C virus antibody, and HIV antibody,
- d. Perform FSH (serum) test in postmenopausal females only,
- e. Perform serum pregnancy tests at Screening, Day -1, and Day 45 females only,
- f. Randomize subjects on Day 1 only,
- g. A single dose of study drug will be administered via SC injection on Days 1, 8, and 15,
- h. Vital signs will be obtained at Screening; on Day -1; on Day 1 within 60 minutes prior to study drug administration and at 15 minutes (±5 min), 1 hour (±10 min) and 2 hours (± 10 min) post-dose; and at 24, 72 and 144 hours (±30 min) post-dose on Days 2, 4, 7, 8, 9, 11, 14, 15, 16, 18, and 21; and on Days 30 (±1 day), and 45 (±1 day),
- i. A complete PE will be performed at Screening and targeted PEs will be performed on Days -1, 1, 2, 4, 7, 8, 9, 11, 14, 15, 16, 18, 21, 30 (± 1 day), and 45 (±1 day),
- j. ECGs will be obtained at Screening and on Day 1 within 30 minutes prior to study drug administration, and 4 hours (± 10 minutes) post-dose (Days 1, 8, and 15), Day 21, Day 30, Day 45, and Unscheduled visits
- k. Fasting (at least 8 hours) blood samples will be collected for hematology, coagulation and chemistries at Screening and on Days -1, 2, 9, 16, 7, 14, 21 and 45 (±1 day). Hematology tests consist of CBC with differential; coagulation tests consist of PT/PTT/INR; Chemistries panel includes albumin, glucose, blood urea nitrogen or urea, potassium, calcium, sodium, chloride,

total protein, creatinine, CO₂, CK, phosphorus, alkaline phosphatase, AST, ALT, total bilirubin, direct bilirubin,

- l. Urine will be collected for urinalysis, urine drug screen and urine alcohol at Screening, and on Day -1. Urine will be collected for urinalysis on Days 2, 7, 9, 14, 16, 21, and 45 (± 1 day),
- m. Blood for PK analysis (plasma) will be drawn pre-dose within 60 minutes before study drug dosing and at 0.5 h (± 5 min), 1 h (± 10 min), 2 h (± 10 min), 4 h (± 10 min), 6 h (± 10 min), 8 h (± 10 min), and 12 h (± 10 min), (Days 1 and 15); pre-dose within 15 minutes before study drug dosing and at 1 (± 10 min), and 4 hours (± 10 min), on Day 8; 24 hours (± 30 min), on Days 2 and 16; 48 hours (± 30 min) on Days 3 and 17; 96 hours (± 30 min, on Days 5, 12, and 19; and 144 hours (± 30 min) on Days 7, 14, and 21 after dosing; and on Days 30 (± 1 day) and 45 (± 1 day),
- n. Injection site assessment pre-dose and at 1 and 4 (± 10 min), 24, 48, 72, 96, 120, and 144 h (± 30 min) post-dose, Day 30 (± 1 day), and Day 45 (± 1 day). Unscheduled visits are not timed.
- o. Subjects are to be assessed for AEs occurring from the time of the first dose of study drug through Day 45 (± 1 day),
- p. Counsel/reminder on contraceptive use and post-discharge instructions (dietary and medication/nonmedication, vaccine and blood/blood product/sperm donation restrictions); as described in [Section 5.1](#).
- q. Memory Aid issued on Day 1, training on Day 7, and review on Days 30, 45 and at Unscheduled visits.

Table 13: Schedule of Study Procedures and Evaluations for Cohort 11 in BA (Part 3)

Procedures/Day	Screening	Baseline Check-in	Inpatient – Confined to CRU							FU	FU/ET	Unscheduled	
	-28 to -2	-1 and 21	1	2	3	4	5	6	7	14 and 35 (± 1)	52 (± 1)		
			22	23	24	25	26	27	28				
Informed Consent Form ^a	X												
Assessment of Eligibility Criteria	X	X											
Demographics	X												
Height ^b , Weight, BMI	X	X									X		
Review of Medical History	X	X											
Hepatitis and HIV tests ^c	X												
Follicle-stimulating hormone (FSH) test ^d	X												

Procedures/Day	Screening	Baseline Check-in	Inpatient – Confined to CRU							FU	FU/ET	Unscheduled	
	-28 to -2	-1 and 21	1	2	3	4	5	6	7	14 and 35 (±1)	52 (±1)		
			22	23	24	25	26	27	28				
Pregnancy test ^e	X	X									X		
Review of Concomitant Medications	X	X	X		X		X		X	X	X	X	
Study drug randomization just prior to dosing ^f			X										
Administration of study drug ^g			X										
Vital signs ^h	X	X	X	X		X			X	X	X	X	
Physical examination ⁱ	X	X	X	X		X			X	X	X	X	
12-lead ECGs ^j	X		X								X	X	
Blood for hematology & coagulation ^k	X	X		X					X		X	X	
Blood for chemistry panel ^k	X	X		X					X		X	X	
Urine for urinalysis ^l drug screen, alcohol ^l	X	X		X					X		X	X	
Urine cotinine	X	X											
Blood for PK analysis ^m			X	X	X		X		X	X	X	X	
Reactogenicity evaluation ⁿ			X	X	X	X	X	X	X	X		X	
Assess for AEs ^o			X	X	X	X	X	X	X	X	X	X	
Counsel/reminders ^p	X								X	X	X	X	
Memory Aid ^q		X	X						X	X	X	X	

Abbreviations: AE: adverse event; BMI: body mass index; CRU: clinical research unit; ECG: electrocardiogram; FU: follow-up; HIV: human immunodeficiency virus; PK: pharmacokinetic.

- Informed consent will be obtained before initiating any trial-related assessments and procedures,
- Height at Screening only,
- Screen (serum) for hepatitis B surface antigen, hepatitis C virus antibody, and HIV antibody,
- Perform FSH (serum) test for postmenopausal (females only),
- Perform serum pregnancy tests at Screening Day -1 and Day 52 females only,
- Randomize subjects on Day 1 only,
- A single dose of study drug will be administered via SC injection/IV infusion on Days 1 and 22,

- h. Vital signs will be obtained at Screening; on Day -1; on Days 1 and 22 within 60 minutes to study drug administration and at 15 minutes (± 5 min), 1 and 2 hours (± 10 min), post-dose; and on Days 2, 4, 7, 23, 25, 28 (± 30 min) and 14 (± 1 day), 35 (± 1 day), and 52 (± 1 day),
- i. A complete PE will be performed at Screening and targeted PEs will be performed on Days -1, 1, 2, 4, 7, 14, 22, 23, 25, 28, 35, and 52. Days 14, 35, and 52 have (± 1 day) window.
- j. ECGs will be obtained at Screening and on Day 1 within 60 minutes prior to study drug administration, and 4 hours (± 10 minutes) post-dose (SC) and 1 hour (± 10 minutes) post-dose (IV) from start of infusion for IV admin, Day 52, and Unscheduled visits
- k. Fasting (at least 8 hours) blood samples will be collected for hematology, coagulation and chemistries at Screening and on Days -1, 2, 7, 23, 28, and 52 (± 1 day). Hematology tests consist of CBC with differential; coagulation tests consist of PT/PTT/INR; Chemistries panel includes albumin, glucose, blood urea nitrogen or urea, potassium, calcium, sodium, chloride, total protein, creatinine, CO₂, CK, phosphorus, alkaline phosphatase, AST, ALT, total bilirubin, direct bilirubin,
- l. Urine will be collected for urinalysis, urine drug screen and urine alcohol at Screening, and on Day -1. Urine will be collected for urinalysis on Days 2, 7, 23, 28, and 52 (± 1 day),
- m. Blood for PK analysis (plasma) will be drawn pre-dose within 60 minutes before study drug dosing and at 0.5(± 5 min), 1, 2, 4, 6, 8, and 12 hours (± 10 min) on Days 1 and 22; 24 hours (± 30 min), on Days 2 and 23; 48 hours(± 30 min) on Days 3 and 24; 96 hours (± 30 min), on Days 5 and 26; and 144 hours (± 30 min) on Days 7 and 28 after dosing; and on Days 14 and 35 (± 1 day) and 52 (± 1 day),
- n. Injection site assessment pre-dose and at 1 and 4 (± 10 min), 24, 48, 72, 96, 120, and 144 h (± 30 min) post-dose, Day 14 (± 1 day), and Day 35 (± 1 day). Unscheduled visits are not timed.
- o. Subjects are to be assessed for AEs occurring from the time of the first dose of study drug through Day 52 (± 1 day),
- p. Counsel/reminder on contraceptive use and post-discharge instructions (dietary and medication/nonmedication, vaccine and blood/blood product/sperm donation restrictions); as described in **Section 5.1**.
- q. Memory Aid issued on Day 1, training on Day 7 (refresher on Day 28), reviewed on Days 21, 14, 35, 52 and at Unscheduled visits.

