6.4.10 Day 30 (± 1 Day) – Follow-Up – Final Study Visit

- Obtain resting vital signs after being at rest for at least 5 minutes.
- 12-lead ECG after at least 5 minutes in the supine position (triplicate readings, at least 1 minute apart within a 15-minute period).
- Perform targeted PE.
- Obtain weight, calculate BMI.
- Obtain blood for hematology/coagulation/chemistry and urine for urinalysis.
- Perform serum pregnancy test (females of childbearing potential only).
- Obtain PK blood sample. No PK blood samples collected in Cohort 1.
- Assess reactogenicity at SC injection site(s) (see [Section 7.1.3](#) and MOP for this study).
- Assess AEs.
- Review Memory Aid.
- Review and record any concomitant medications and non-pharmacologic treatments/procedures since admission to the CRU.
- Review post-study instructions (contraceptive use, pregnancy reporting).

6.5 Part 2 (Cohorts 7 through 10)**6.5.1 Days 1, 8, and 15 – Inpatient CRU**

Study drug or placebo will be administered via SC injection in the morning on Days 1, 8, and 15. Subjects will be inpatients in the CRU and will undergo the following procedures, which are listed in the Schedule of Study Procedures and Evaluations ([Appendix A](#)) and detailed in Clinical Evaluations ([Section 7](#)):

- Randomize the subject (Day 1 only).
- Review inclusion criteria numbers 2-7 and 10-11, and exclusion criteria numbers 2-4 and 8-18 (from [Section 5.1.2](#)) to ensure the subject remains eligible for dosing (Days 8 and 15 only).
- Obtain resting vital signs before study drug dosing (within 60 minutes of study drug dosing for Day 1). This is to be documented as the Baseline prior to dosing on Day 1.
- Perform targeted PE.
- Obtain a 12-lead ECG before study drug dosing (Day 1 only) after at least 5 minutes in the supine position (triplicate readings, at least 1 minute apart within a 15-minute period) and within 60 minutes before study drug dosing.
- Baseline (Day 1) and pre-dose (Days 8 and 15) skin assessment at SC injection site area(s) prior to study drug dosing (see [Section 7.1.3](#) and MOP for this study).
- Administer study drug via SC injection in the abdomen at a slow, steady pace.
- Obtain vital signs at 15 minutes (± 5 min), 1 hour (± 10 min), and 2 hours (± 10 min) after dosing, after resting in a supine or semi-supine position for at least 5 minutes.

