7.1.5 Vital Signs

Vital signs (body temperature, heart rate, respiration rate, and blood pressure) will be obtained at times specified in [Appendix A](#). Vital signs will be measured after resting at least 5 minutes. The pre-dose vital signs on days of dosing will be measured within 60 minutes of study drug dosing; Day 1 post-dose vital signs measurements should be taken within \pm 5 minutes of the 15-minute post-dose timepoint and within \pm 10 minutes for additional post-dose timepoints. Other vital signs during the inpatient stay will be taken within \pm 30 minutes of the nominal timepoint. For outpatient visits, vital signs will be measured within the visit window.

Day 1 post-dose timepoints for vital sign measurements for the IV portion of Part 3 will be based on the start of infusion.

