7.1.6 Electrocardiograms

Standard 12-lead ECGs to assess heart rate, rhythm, and PR, QRS, QT, and QTc interval durations will be obtained at times specified in [Appendix A](#).

ECGs (triplicate readings, at least 1 minute apart within a 15-minute period), will be taken after at least 5 minutes in the supine position. The pre-dose ECGs on days of dosing will be taken within 60 minutes of study drug dosing. Post dose ECGs on days of dosing will be taken at 4 hours (\pm 10 minutes) after SC dosing. Post dose ECGs on days of dosing will be taken at 1 hour (\pm 10 minutes) from start of infusion for IV administration in Part 3.

ECGs will also be taken at the following timepoints:

- Day 7, Day 30, and Unscheduled visits for SAD
- Day 21, Day 30, Day 45, and Unscheduled visits for MAD
- Day 52 and Unscheduled visits for BA

The screening ECG will be used by the PI to determine a subject's eligibility for enrolment. The Day 1 pre-dose ECG will be reviewed to determine if subjects can be dosed.

All ECGs will be reviewed by the PI or designee. ECGs with the following readings will be considered acceptable for trial participation and will not be considered abnormal for trial purposes unless the PI or physician designee believes they represent a new medical condition when compared to baseline ECGs. In such cases an AE will be documented, and the subject will be followed for safety evaluations as appropriate. The following pre-existing conditions identified at enrolment will not be considered AEs:

- Sinus bradycardia,
- Sinus arrhythmia,
- Subjects without a history of prolonged QTc and an abnormal QTc interval at Screening will undergo repeat ECG assessment within the screening period before randomization to confirm prolongation. If the repeat ECG QTcF is within normal limits (see [Appendix B](#)) the subject may be considered for enrolment.

The Sponsor may review all or individual screening ECGs or may delegate to determine if meets intention of entry criteria goal of enrolling healthy normal subjects.

If a subject has possible cardiac-related symptoms, repeat ECGs will be obtained every 30 minutes (± 3 minutes) until the waveform reverts to its baseline appearance, or symptoms resolve, or are determined not to be cardiac-related. Subjects with cardiac-related symptoms that are associated with ECG changes will be transferred to appropriate emergency department for further evaluation and treatment at the discretion of the PI.

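### In Part 2, Table 12 ties the 15-min, 1-h and 2-h post-dose vital signs to Day 1 while Section 6.5.1 asks for them on Days 1, 8 and 15, so the schedule sets no timed reading in the first 24 h after doses 2 and 3

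*Protocol*

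**What the plan says.** **Dosing.** Table 12 footnote g states: "A single dose of study drug will be administered via SC injection on Days 1, 8, and 15".

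**Procedure text.** Section 6.5.1 is one list for all three dosing days: "Study drug or placebo will be administered via SC injection in the morning on Days 1, 8, and 15". It asks for vital signs at 15 min (±5), 1 h (±10) and 2 h (±10) after dosing, with no limit by day. Other items in the list do carry limits: randomization and the pre-dose ECG are for Day 1, the eligibility re-check is for Days 8 and 15, and the reduced PK sampling is for Day 8.

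**Schedule.** Table 12 footnote h gives the pre-dose and early readings "on Day 1 within 60 minutes prior to study drug administration and at 15 minutes", 1 h and 2 h. It then gives readings at 24, 72 and 144 h "post-dose on Days 2, 4, 7, 8, 9, 11, 14, 15, 16, 18, and 21".

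**Evaluation text.** Section 7.1.5 refers to Appendix A for the times of vital signs. It gives the ±5 and ±10 min post-dose windows for Day 1 and ±30 min for other inpatient readings. For Part 3 it adds: "Day 1 post-dose timepoints for vital sign measurements for the IV portion of Part 3 will be based on the start of infusion".

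**Comparable footnotes.** The Part 3 counterpart, Table 13 footnote h, names both dosing days: "on Days 1 and 22 within 60 minutes to study drug administration and at 15 minutes". Table 12 footnote j names Days 1, 8 and 15 for the 4-h post-dose ECG. For the pre-dose ECG it says "on Day 1 within 30 minutes prior to study drug administration", whereas Section 7.1.6 says "The pre-dose ECGs on days of dosing will be taken within 60 minutes of study drug dosing" and Section 6.5.1 also uses 60 min.

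**The concern.** The procedure text and the schedule prescribe different monitoring after the second and third doses, and the protocol has no rule on which governs. Section 6.5.1 says its procedures are those listed in Appendix A, and Section 7.1.5 also points to Appendix A for times. A site that builds its worksheets from Table 12 would be following the protocol as it reads it.

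Vital signs are a stated Part 2 primary safety measure (Section 3.3.1), and Section 10.5.2 summarizes change from baseline by time point. Repeat dosing is what Part 2 adds to Part 1, and Section 2.3.1 describes this as the first human study by the SC route. If the early readings were taken after dose 1 only, the early vital-sign response to doses 2 and 3 could not be compared with that to dose 1. A graded change in that window, which could count toward the halting rules in Section 8.7.2, would also depend on a reading at an unspecified time.

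**Working it through.** **1. Do the days in footnote h match its hours?** Inputs: doses on Days 1, 8 and 15 (footnote g); hours 24, 72 and 144 (footnote h). Formula: study day = dose day + hours/24.

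| Dose day | 24 h | 72 h | 144 h |
|---|---|---|---|
| 1 | 1+1 = 2 | 1+3 = 4 | 1+6 = 7 |
| 8 | 8+1 = 9 | 8+3 = 11 | 8+6 = 14 |
| 15 | 15+1 = 16 | 15+3 = 18 | 15+6 = 21 |

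This gives nine days. The footnote lists eleven, so its list is not reproduced; the two extra days are 8 and 15. Day 8 is (8−1)×24 = 168 h after dose 1 and 0 h after dose 2. Day 15 is (15−8)×24 = 168 h after dose 2 and 0 h after dose 3. No stated hour fits either day, so the schedule requires a reading on each without saying when.

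**2. How many early sets differ?**

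- Section 6.5.1: 3 timepoints × 3 doses = 9 per subject.
- Footnote h: 3 timepoints × 1 dose = 3 per subject.
- Difference: 9 − 3 = 6 per subject, and 6/9 = 67%.
- Over the planned Part 2 enrolment (Table 2: 32 subjects, 24 on rezafungin): 6 × 32 = 192 sets, of which 6 × 24 = 144 are on active drug.

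**3. What stays scheduled after doses 2 and 3 if footnote h is followed?**

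- The 24, 72 and 144 h vital signs on Days 9, 11, 14, 16, 18 and 21.
- A reading on Days 8 and 15 at no defined hour. Footnote h and the table grid both call for it, and footnote i schedules a targeted examination on those days, which Section 7.1.3 says includes vital signs.
- A triplicate ECG 4 h after each dose, from which heart rate is read (Section 7.1.6).

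What is missing is any vital-sign set at a defined time between dosing and 24 h.

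**4. Does Section 7.1.5 settle it?** No. Its tight windows are for Day 1. A 15-min reading taken on Day 8 would fall under its general ±30 min window, which runs from 15−30 = −15 min (before the dose) to 15+30 = 45 min. Section 6.5.1 gives 10 to 20 min for the same reading.

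**5. Two related mismatches.**

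- *Part 2 pre-dose ECG:* a tracing taken 31 to 60 min before dosing complies with Sections 6.5.1 and 7.1.6 but is outside the 30 min in Table 12 footnote j.
- *Part 3 infusion:* Section 7.1.5 limits the start-of-infusion rule to Day 1, yet the five SC→IV subjects (Table 3) are infused on Day 22. Section 6.6.1, headed Days 1 and 22, already times the IV vital signs from the start of infusion, so only the wording of 7.1.5 is out of line.

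**The case against.** The strongest reply is that Section 6.5.1 is explicit. It covers confined inpatients, gives its own windows, and marks day limits where it means them. Omitting the readings would be a deviation from the protocol body, so a careful site would take them and little would be lost. This stands in part: it makes 192 a ceiling, not an expected loss. It does not remove the contradiction, because the schedule is equally part of the protocol and neighbouring footnotes name every dosing day when they mean every dosing day.

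Several stronger readings are tempting, and the documents do not support them:

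- *That no vital signs at all would be taken from dosing until 24 h after doses 2 and 3.* The schedule does require a reading on Days 8 and 15; only its hour is undefined.
- *That tachycardia would go unmeasured.* The 4-h ECG records heart rate after every dose, and adverse events are assessed on each dosing day.
- *That the by-time-point summary would be empty for two of the three doses.* The 24, 72 and 144 h readings remain, and Section 10.5.2 does not itself name the early Part 2 timepoints.
- *That the Day 22 infusions have no timing rule.* Section 6.6.1 supplies it.

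The risk argument also needs restraint. Section 2.3.1 describes the histamine-type reactions for IV rezafungin and for rapid echinocandin infusions. The risks it names for SC dosing are local, and injection sites are checked at 1 h and 4 h after each dose.

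**Conclusion.** The inconsistency is real and the text is wrong as written. Footnote h contradicts Section 6.5.1 on the early post-dose vital signs for doses 2 and 3, and it assigns two dosing days to hours that cannot fall on them. Read literally, the schedule leaves no vital signs at a defined time in the first 24 h after those doses: up to 6 of 9 early sets per subject, at most 192 in all.

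That maximum assumes 32 subjects, all receiving three doses, no replacements, and a site that follows Table 12 in preference to Section 6.5.1 throughout.

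A reader might also infer that trial results are compromised. They are not: SAP Section 1 states that no subject entered any MAD or BA cohort, and the SAP analyses only SAD Cohorts 1 and 2. The defect lies in the protocol text and would matter if that text were reused. Nor do the documents establish which monitoring schedule was intended; they establish only that the passages must be reconciled.

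**What to change.** - Reconcile Table 12 footnote h, Section 6.5.1 and Section 7.1.5 so that all three give the same dosing days, timepoints and windows for post-dose vital signs in Part 2. Keep the windows explicit.
- Take Days 8 and 15 out of the 24/72/144 h list in footnote h, and state when the readings on those days are due.
- Align the Day 1 start-of-infusion wording in Section 7.1.5 with Section 6.6.1, which already covers Day 22.
- Give one Part 2 pre-dose ECG window in Table 12 footnote j, Section 6.5.1 and Section 7.1.6.

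The cost is protocol wording. If the early readings were kept for all three doses, Section 6.5.1 already asks for them, so no procedure would be added. With Part 2 never enrolled, no reanalysis follows.
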